9.3. Sample Size Calculation

The sample size was calculated to estimate the sensitivity of the LaserSAFE technique with a 95% confidence interval and a precision of $\pm 5\%$. Assuming an expected sensitivity of 91% and a positive margin prevalence of 20%, at least 126 disease-positive participants are required. This corresponds to a total of 630 participants. Allowing for up to 10% missing or non-evaluable data, the adjusted target sample size is 693 participants.

The assumptions for sample size calculations were based on the results of our previous studies where LaserSAFE demonstrated in blinded analysis of a small cohort of patients a sensitivity of 91% to detect positive margins.

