These studies required slicing the prostate margins before sampling, which required the presence of pathologist to perform and complicated subsequent pathological assessment. To overcome this, we developed LaserSAFE, a standardised technique for assessing intact specimens using FCM (25). In a pilot study, LaserSAFE demonstrated encouraging sensitivity across both expert and novice readers blinded to final histopathology results (26). More recently, we completed a feasibility study comparing LaserSAFE and NeuroSAFE, showing 91% sensitivity for detecting margins greater than 0.5 mm. However, we could not expand the feasibility study to other sites due to challenges associated with adopting NeuroSAFE in other National Health Service (NHS) centres.

The available evidence supports LaserSAFE as a promising alternative to NeuroSAFE, sharing the same underlying goal of enabling safe nerve-sparing in patients who might otherwise not receive it. The NeuroSAFE PROOF study has already demonstrated, with level 1 evidence, that this approach

can lead to improved patient outcomes (17). However, as previously reported and confirmed in our feasibility study, implementing NeuroSAFE in the NHS is not currently feasible due to the resource and time demands required.

Several important knowledge gaps must be addressed before LaserSAFE can be safely introduced into clinical practice. Unlike standard FFPE analysis, LaserSAFE evaluates tissue en face rather than in cross-section (19). This change in orientation presents a challenge for pathologists, who must adapt to interpreting margins from a new perspective. Therefore, the most critical parameter to assess is the sensitivity of the technique, as false-negative results, or failing to detect a PSM, could expose patients to adverse oncological outcomes.

An important caveat is, that evidence suggests that the length of a PSM correlates with the risk of recurrence, with margins smaller than 2 mm not associated with increased recurrence risk (27). Consequently, the NeuroSAFE protocol recommends secondary resection only when the PSM exceeds 2 mm, representing a clinically significant margin. However, margins assessed en face appear larger than those evaluated in cross-section, due to differences in orientation and tissue shrinkage during frozen or paraffin processing. Resecting small, non-significant margins could therefore compromise functional outcomes without providing oncological benefit.

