9. STATISTICAL CONSIDERATIONS

9.1. Primary Outcome

The primary objective is to evaluate the accuracy of using the LaserSAFE technique to evaluate margin status during radical prostatectomy compared to the FFPE. The primary endpoint will be the sensitivity of LaserSAFE to detect positive margins in the posterolateral area of the prostate of more than 3 mm.

- Sensitivity will be monitored across the trial when the first 50, 150, 300 and 500 participants have been recruited.
- If sensitivity decreases below 85%, trial methodology will be reviewed and if considered appropriate by the trial will be stopped.
- This would minimise the risk of introducing an inferior alternative that would put patients at risk worse oncological outcomes

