9.6.2. Primary outcome analysis

The primary analysis will evaluate the sensitivity of LaserSAFE interpretation for detecting positive surgical margins greater than 3 mm in the posterolateral prostate, using FFPE histopathology as the reference standard.

Interim analyses of sensitivity will be conducted after recruitment of the first 50, 150, 300, and 500 participants. If the observed sensitivity falls below % at any interim analysis, the trial will be stopped for futility. The final analysis will be undertaken once the target sample size of 693 participants has been reached. Sensitivity will be reported with a two-sided 95% confidence interval, calculated using the Wilson score method. Indeterminate or missing LaserSAFE results will be considered non-diagnostic and classified as false negatives in the primary analysis.

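### Section 9.3 does not size the trial on its primary endpoint: unless margins >3 mm occur in about 20% of men, or sensitivity for them is well above 91%, 693 men will not give ±5%

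*Protocol*

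**What the plan says.** Section 9.3 sets the sample size "to estimate the sensitivity of the LaserSAFE technique with a 95% confidence interval and a precision of" ±5%. Its inputs and first result are: "Assuming an expected sensitivity of 91% and a positive margin prevalence of 20%, at least 126 disease-positive participants are required". It continues: "This corresponds to a total of 630 participants". The last step is: "Allowing for up to 10% missing or non-evaluable data, the adjusted target sample size is 693 participants". It attributes the sensitivity to earlier work that showed "in blinded analysis of a small cohort of patients a sensitivity of 91% to detect positive margins".

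The endpoint is narrower. Section 9.1: "The primary endpoint will be the sensitivity of LaserSAFE to detect positive margins in the posterolateral area of the prostate of more than 3 mm". Section 9.6.2 describes the primary analysis as the "sensitivity of LaserSAFE interpretation for detecting positive surgical margins greater than 3 mm in the posterolateral prostate", with FFPE histology as the reference standard and a Wilson 95% interval. Sections 3.3, 9.2 and 9.6.3 list accuracy for margins of any length separately, as a secondary outcome.

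Two other places bear on the inputs. Section 2 describes a feasibility study "showing 91% sensitivity for detecting margins greater than 0.5 mm". The statistical methodology entry of the Study Summary puts the primary analysis on a per-side basis, whereas 9.3 counts participants.

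**The concern.** The precision of a sensitivity estimate depends on how many reference-positive units there are and on the sensitivity itself. For the primary endpoint, the reference-positive units are posterolateral FFPE margins >3 mm. These are a subset of all positive margins, and the protocol itself treats the two targets separately. Section 9.3 uses a prevalence and a sensitivity for positive margins without saying that either refers to that subset.

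If the 20% covers positive margins of any length or site, the primary denominator is smaller than 126 and the interval is wider than stated. Section 2 calls sensitivity the most critical parameter, because a missed margin can harm the patient. The precision claimed for it should therefore belong to the endpoint that will be reported.

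**Working it through.** **Inputs.** From 9.3: sensitivity p = 0.91, half-width d = 0.05, 95% confidence (z = 1.96), prevalence 0.20, loss 10%. From 9.6.2: Wilson interval. The prevalence of posterolateral FFPE margins >3 mm is not given. I assume 20%, 15%, 10% and 6%. The sensitivity for such margins is not given either. I use 91% and, as an assumption, 95%.

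**Step 1: reproduce the plan.** Positives needed = z²p(1−p)/d² = 1.96² × 0.91 × 0.09 / 0.05² = 125.8, rounded up to 126. Total = 126/0.20 = 630. Inflated = 630 × 1.10 = 693. All three figures reproduce.

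**Step 2: slack.** This formula is the normal-approximation (Wald) one, and 126 positives meet ±5.00 points exactly. At 91% sensitivity, any >3 mm prevalence below 126/630 = 20% misses the target. If all 693 men are evaluable, the limit is 126/693 = 18.2%.

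**Step 3: precision for the endpoint.** The Wilson half-width is z√[p(1−p)/n + z²/(4n²)] / (1 + z²/n), with n = 630 × prevalence.

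| >3 mm prevalence (assumed) | Positives n | Half-width at 91% (interval) | Half-width at 95% |
|---|---|---|---|
| 20% | 126 | 5.07 (84.7 to 94.9) | 3.98 |
| 15% | 94.5 | 5.88 (83.5 to 95.3) | 4.65 |
| 10% | 63 | 7.25 (81.4 to 95.9) | 5.83 |
| 6% | 37.8 | 9.48 (77.7 to 96.7) | 7.81 |

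**Step 4: how far a higher sensitivity helps.** At 95%, the plan's formula needs 1.96² × 0.95 × 0.05 / 0.05² = 73 positives, a prevalence of 73/630 = 11.6%. Under the Wilson formula above, n = 83 brings the half-width to 5.0, a prevalence of 83/630 = 13.2%. Below that, even 95% sensitivity does not give ±5%.

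**Step 5: a pull in the other direction.** Section 9.6.2 counts indeterminate or missing LaserSAFE results as false negatives. If the 91% refers to readable images and 5% of results are unreadable (both assumptions), expected sensitivity is 0.91 × 0.95 = 86.5%. The formula then asks for 1.96² × 0.8645 × 0.1355 / 0.05², about 180 positives.

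**Scale.** Holding 126 positives at a 10% prevalence would take 126/0.10 = 1,260 evaluable men, twice the plan's 630. This only shows the size of the gap; I do not propose it.

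**The case against.** The best defence is that 9.3 never calls its 20% an overall prevalence. Its term for the required men, disease-positive, can be read as positive by the endpoint's own definition. The cohort is also selected: men advised against intrafascial sparing on at least one side (5.1), who then have intrafascial dissection on both sides (6.3.1.1). Nothing in the protocol rules out 20% for margins >3 mm. Larger margins may also be easier to see, so holding sensitivity at 91% shows only one side of the uncertainty. Bilateral positives would add some correlated units to a per-side analysis.

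All of this stands, and it makes the shortfall conditional. It does not supply the missing basis: the reader still cannot tell whether either input belongs to the primary endpoint.

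Four stronger readings are tempting, and the protocol does not support them:

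- **That 693 men will certainly miss ±5%.** This needs a >3 mm prevalence that the protocol does not give.
- **That the 91% is the figure for margins >0.5 mm.** Section 2 describes a blinded pilot and a separate feasibility study, and gives the 91% for the latter. Section 9.3 cites a blinded small cohort. They may or may not be the same source.
- **That the mismatch is why the interval may fail to exclude 85%.** With the full 126 positives and 91% observed, the Wilson lower limit is already 84.7%. Section 9.3 is sized on precision alone, and sections 3.3 and 9.1 use 85% as a monitoring trigger for review and possible stopping, not as a success criterion.
- **That the inflation step matters materially.** Dividing, 630/0.90 = 700, differs from 693 by 1%. A full 10% loss from 693 leaves about 624 men and 124.8 positives, or ±5.02 by the plan's formula. Missing LaserSAFE results also stay in the denominator under 9.6.2. This is a side note at most.

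**Conclusion.** The point holds in conditional form. The arithmetic of 9.3 is correct on its own inputs; the fault is that those inputs are not stated for the primary endpoint. As written, the ±5% is unsupported for posterolateral FFPE margins >3 mm.

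The claim survives if the >3 mm prevalence is about 20%, or if sensitivity for such margins is well above 91% and the prevalence is not too low. Otherwise the half-width at 91% sensitivity runs from about 6 points at 15% prevalence to about 9.5 at 6%. These sizes rest on 630 evaluable men, one unit per man, and assumed prevalences. I am confident of the mismatch; the size of the shortfall cannot be fixed from the protocol.

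**What to change.** In section 9.3:

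1. State the prevalence and expected sensitivity for posterolateral FFPE margins >3 mm, from the sponsor's earlier data where these exist and otherwise as a stated range. Say which study and which margin definition the 91% comes from.
2. Use the same unit as the primary analysis. Reconcile the per-side wording of the Study Summary with the participant count in 9.3 and, if the unit is the side, say how two sides from one man are handled.
3. Replace the single ±5% with the Wilson half-width that 693 men deliver, after the expected loss, over a small grid of prevalence and sensitivity such as the one above. Allow for unreadable results counted as false negatives.

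The 630 × 1.10 step can be tidied in the same edit. The cost is a rewording of one section and probably a less favourable stated precision. No extra enrolment is needed, and no clinical rule changes.

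### Section 9.3: 693 covers a 9.1% loss rather than 10%, 126 positives is an expected count, and the ±5% is a Wald figure while 9.6.2 uses Wilson; the effect on precision is small

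*Protocol*

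**What the plan says.** Section 9.3 plans for precision. It assumes 91% sensitivity, a positive-margin prevalence of 20%, and a 95% confidence interval of ±5 percentage points. From these it concludes that "at least 126 disease-positive participants are required", and continues: "This corresponds to a total of 630 participants". It then adds the loss allowance: "Allowing for up to 10% missing or non-evaluable data, the adjusted target sample size is 693 participants". The figure 693 also appears in the Study Summary and in section 9.6.2.

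Section 9.6.2 fixes the interval for the primary analysis: "Sensitivity will be reported with a two-sided 95% confidence interval, calculated using the Wilson score method". It also fixes how missing index results are treated: "Indeterminate or missing LaserSAFE results will be considered non-diagnostic and classified as false negatives in the primary analysis".

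Sections 3.3 and 9.1 use 85% sensitivity as the level below which the trial's methodology is to be reviewed.

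**The concern.** Section 9.3 contains no hypothesis test and no power statement, so precision is the whole justification for 693. Three steps in that justification do not quite fit together.

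- The loss allowance is applied by multiplying up, not by dividing by the retained fraction.
- A minimum number of positives is converted to a total as if prevalence were exact, although the number of positives will vary.
- The number of positives comes from a symmetric interval formula that the analysis will not use.

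At stake is whether 91% ±5% describes the interval the trial will report. Someone reading that statement expects a lower limit of 86%.

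**Working it through.** **Inputs.** From section 9.3: sensitivity p = 0.91, precision d = 0.05, 95% confidence (z = 1.96), prevalence 0.20, loss up to 10%. From section 9.6.2: two-sided 95% Wilson interval.

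**Reproducing the plan's figures.**
- Wald formula: n = z²p(1−p)/d² = 1.96² × 0.91 × 0.09 / 0.05² = 125.85, rounded up to 126.
- Total: 126/0.20 = 630.
- Allowance: 630 × 1.10 = 693.

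All three stated figures reproduce, which shows that the Wald formula and the multiplicative inflation were used.

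**Step 1: the loss allowance.**
- Loss that 693 can absorb while keeping 630: (693 − 630)/693 = 63/693 = 9.1%.
- After a 10% loss: 693 × 0.90 = 623.7 men, and 623.7 × 0.20 = 124.7 expected positives.
- Number needed: 630/0.90 = 700, so the shortfall is 7.
- Effect on the Wald half-width at 91%: 5.00 points with 126 positives, 5.02 points with 124.7.

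**Step 2: 126 as an expected count.** With prevalence exactly 20%, the number of positives is binomial.

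| Scenario | Mean positives | P(126 or more) |
|---|---|---|
| 630 evaluable | 126.0 | 52% |
| 693 less 10% | 124.7 | 47% |
| 700 less 10% | 126.0 | 52% |
| 693, no loss | 138.6 | 89% |

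With 693 less 10%, the central 95% range of positives is 105 to 145. Writing 700 corrects step 1 but leaves the chance of reaching 126 at about one half. Low counts cost little: at the 5th percentile for 624 men (109 positives) the Wald half-width is about 5.4 points.

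**Step 3: Wilson against Wald.** The Wilson limits are [p + z²/2n ± z√(p(1−p)/n + z²/4n²)] / (1 + z²/n). At p = 0.91 and n = 126:
- limits 84.7% to 94.9%;
- half-width 5.07 points (Wald: 5.00);
- 6.3 points below 91% and 3.9 above.

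A Wilson half-width of 5 points or less at 91% needs 130 positives.

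**Step 4: how much of this is due to Wilson.** Take 693 less 10%, true sensitivity 91%, and let both the positives and the detections vary. The Wilson half-width is then 5 points or less in 46% of trials and 5.5 points or less in 75%. The Wald half-width is 5 points or less in 51%. Most of the shortfall from certainty therefore comes from planning on an expected count; the choice of interval adds little.

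**Step 5: which losses shrink the denominator.** Under section 9.6.2, missing or indeterminate LaserSAFE results stay in as false negatives. Only missing reference results and withdrawals reduce the count of positives. If, as an illustration, the whole 10% were missing LaserSAFE results, the denominator would keep its 138.6 expected positives. Expected sensitivity would then fall to 0.91 × 0.90 = 81.9%, with a Wald half-width of about 6.4 points.

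**The case against.** The strongest reply is that none of this is large. Seven men is 1% of the sample, the stated loss is a ceiling, and a Wilson half-width of 5.07 is ±5 for practical purposes. That stands, and it sets the weight of the point.

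Dividing required positives by prevalence is also common practice. Section 9.3 says that 126 are required and that this corresponds to 630; it does not guarantee that 630 men will yield 126. A reader might infer a broken promise, but the text supports only the narrower statement that a minimum was converted through an average. The 47% is also a pessimistic case, because it assumes the full 10% leaves the denominator. With no such loss the figure is 89%. The binomial counts are of men, as in section 9.3, whereas the Study Summary describes the primary analysis as per side. If 20% is a per-man prevalence, bilateral positives would add to the analysed count.

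A reader might go further and infer from the 84.7% lower limit that the design fails its own safety criterion. The documents do not support that. The 85% level in sections 3.3 and 9.1 applies to sensitivity itself, and section 9.6.2 refers to the observed value. No rule uses a confidence limit, and no criterion is set for the lower arm. Nor would the limit usually fall below 85%: with true sensitivity 91%, it does so in 53% of trials with 693 less 10% and 48% with no loss, close to an even chance. At 126 positives it turns on a single case: 114 detected gives a lower limit of 84.1%, 115 gives 85.04%. Under Wald it would still fall below 85% in 36% of trials, so much of this is ordinary sampling variation.

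Keeping missing LaserSAFE results in the denominator does not rescue the stated precision, because it lowers expected sensitivity (step 5).

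**Conclusion.** The point holds as a minor correction. On the Protocol's own inputs, 693 allows for 9.1% loss and 700 would be needed for 10%. The 126 is an expected count, reached in about half of trials at the planned evaluable size. The ±5 points is a Wald figure, while the specified Wilson interval at 91% and 126 positives runs from 84.7% to 94.9%. Its half-width is almost as stated, but it is asymmetric, with a lower limit close to the 85% monitoring level. No estimate, decision rule or stopping rule changes.

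These results assume 20% prevalence and 91% sensitivity as stated, one binomial outcome per man, and, where a 10% loss is applied, that all of it leaves the denominator.

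**What to change.** Either of two changes to section 9.3 is enough.

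1. Keep recruitment at 693 and reword along these lines: *693 participants allow for about 9% loss; 126 is the expected number of positives among 630 evaluable men; at an observed sensitivity of 91% the expected Wilson 95% interval is about 85% to 95%.*
2. Keep the 10% allowance and write 700 in section 9.3, section 9.6.2 and the Study Summary. The wording on the expected count and the Wilson interval is still needed, because 700 does not alter either.

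In both cases, state that the allowance refers to missing reference results or withdrawals, since section 9.6.2 retains missing LaserSAFE results as false negatives.

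The first option costs only wording and makes the stated precision slightly less favourable. The second adds seven participants.

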9.4. Planned Recruitment Rate

This study will take place in high volume centres across the UK where more than 300 RARPs are performed each year. Given that in the BAUS UK national dataset (29) more than 70% of patients undergoing RARP do not receive bilateral nerve-sparing a large pool of potential recruits is expected at each site. Therefore, we expect to recruit at least 12 patients every month to be able to finish the recruitment phase of the study within 60 months. This recruitment rate is similar to the one observed during the NeuroSAFE PROOF trial.

9.5. Randomisation Methods

Randomisation will not be done in this trial.

9.6. Statistical Analysis

9.6.1. Summary of Baseline Data and Flow of Participants

Baseline variables that will be collected include age at diagnosis, weight, height, self-reported ethnicity, PSA at diagnosis, MRI PIRADS/Likert score, T stage, prostate volume, nerve sparing recommendation, biopsy grade group and histological subtype. Variables registered at the time of the intervention are outlined in the CRF.

9.6.2. Primary outcome analysis

The primary analysis will evaluate the sensitivity of LaserSAFE interpretation for detecting positive surgical margins greater than 3 mm in the posterolateral prostate, using FFPE histopathology as the reference standard.

Interim analyses of sensitivity will be conducted after recruitment of the first 50, 150, 300, and 500 participants. If the observed sensitivity falls below % at any interim analysis, the trial will be stopped for futility. The final analysis will be undertaken once the target sample size of 693 participants has been reached. Sensitivity will be reported with a two-sided 95% confidence interval, calculated using the Wilson score method. Indeterminate or missing LaserSAFE results will be considered non-diagnostic and classified as false negatives in the primary analysis.

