	
 • MRI informed very low likelihood for extra prostatic extension in the proximity of NVB (Based on EPE Likert 1 score or tumour away from the posterolateral areas of the prostate) • MRI informed high likelihood for extra prostatic extension in the proximity of NVB (based on Likert 5 score or bulging tumour on MRI T2 images) • Patients in whom preoperative imaging shows rectal involvement or seminal vesicle invasion in which nerve-sparing is deemed not feasible due to oncological safety concerns. • Patients who received previous treatment for prostate cancer: External beam radiotherapy, brachytherapy, focal therapy, chemotherapy.
Statistical methodology and analysis:	
Statistical analysis
 
The primary analysis will evaluate the sensitivity of LaserSAFE to diagnose positive surgical margins per side against the final paraffin analysis. Specificity and positive and negative predictive values will be reported. Measures of accuracy will be presented with 95% confidence intervals. A definitive protocol for statistical analysis will be finalised before recruitment is finished.

Funding & Other	
Funding:	UCLH Charity Number 7298
Other support:	SamanTree Medical SA
Key Study Contacts TBD	
Committees	TMG
Sub-contractors	None

KEY ROLES AND RESPONSIBILITIES

SPONSOR: The sponsor is responsible for ensuring before a study begins that arrangements are in place for the research team to access resources and support to deliver the research as proposed and allocate responsibilities for the management, monitoring and reporting of the research. The Sponsor also must be satisfied there is agreement on appropriate arrangements to record, report and review significant developments as the research proceeds, and approve any modifications to the design.

FUNDER: The funder is the entity that will provide the funds (financial support) for the conduction of the study. Funders are expected to provide assistance to any enquiry, audit or investigation related to the funded work.

CHIEF INVESTIGATOR (CI): The person who takes overall responsibility for the design, conduct and reporting of a study. If the study involves researchers at more than once site, the CI takes on the primary responsibility whether he/she is an investigator at any particular site.

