3.3. Outcome Measures/Endpoints

- Primary endpoint
 - Sensitivity of LaserSAFE to detect positive margins in the posterolateral area of the prostate of more than 3 mm
 - Sensitivity will be monitored across the trial when the first 150, 300 and 500 participants have been recruited.
 - If sensitivity decreases below 85%, trial methodology will be reviewed and if considered appropriate the trial will be stopped.
- Secondary endpoints
 - Define the cut-off point for triggering secondary resection based on the prevalence of residual prostate cancer in secondary resections.
 - Overall sensitivity, specificity, PPV and NPV of LaserSAFE compared to FFPE analysis for any length of PSM
 - Overall specificity, PPV and NPV of LaserSAFE compared to FFPE analysis for any PSM > 3 mm.
 - Rate of residual prostate cancer in secondary resections of the neurovascular bundle
 - Prevalence of PSM detected by paraffin analysis in the overall cohort.
 - Prevalence of PCa biochemical recurrence or salvage treatment within 12 months after surgery
 - Mean score for EPIC-26 urinary incontinence domain at baseline, 3 and 12 months after surgery
 - Mean score for EPIC-26 erectile function domain at baseline, 3 and 12 months after surgery

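### The interim sensitivity rule is stated in conflicting ways (three or four looks, review or mandatory stop), and a mandatory stop at a raw 85% would trip often in a test with the assumed 91% sensitivity

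*Protocol*

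**What the plan says.** The rule appears three times in the protocol.

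- **Section 3.3 (Outcome Measures/Endpoints):** "Sensitivity will be monitored across the trial when the first 150, 300 and 500 participants have been recruited". Sensitivity below 85% leads to a review of the methodology, with a stop only if that is thought appropriate.
- **Section 9.1 (Primary Outcome):** "Sensitivity will be monitored across the trial when the first 50, 150, 300 and 500 participants have been recruited". The threshold is again 85%, and the consequence is that "trial methodology will be reviewed and if considered appropriate by the trial will be stopped". The stated purpose is to avoid exposing patients to an inferior technique and worse cancer outcomes.
- **Section 9.6.2 (Primary outcome analysis):** the same four looks as 9.1, then "If the observed sensitivity falls below % at any interim analysis, the trial will be stopped for futility". Indeterminate or missing LaserSAFE results count as false negatives. A Wilson interval is named for reporting sensitivity, but the interim trigger is the observed value.

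On timing, the Study Summary says "A definitive protocol for statistical analysis will be finalised before recruitment is finished".

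**The concern.** A team that sees 8 of 10 positive margins detected after 50 participants cannot tell from the protocol whether that look exists. Nor can it tell whether the result calls for a discussion or ends the trial. Section 9.6.2 also labels as futility a rule whose purpose in 9.1 is patient safety.

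A mandatory stop raises a second problem. The trigger is a bare proportion, and at the first look it rests on very few positives. A test that performs exactly as the sample size assumes could be abandoned by chance.

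Finally, the Study Summary's timetable would allow the analysis plan to be completed after every one of these looks. Leaving the conflict to that plan therefore does not guarantee that it is settled before data are seen.

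**Working it through.** **Planning figures (section 9.3).** "Assuming an expected sensitivity of 91% and a positive margin prevalence of 20%, at least 126 disease-positive participants are required". Check, for a 95% interval with half-width 5 points:

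- n = 1.96² × 0.91 × 0.09 / 0.05² = 125.85, rounded up to 126
- 126 / 0.20 = 630
- 630 × 1.10 = 693

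The protocol's figures reproduce.

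**Assumptions for the interim check.**

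- The threshold is 85%, taken from 3.3 and 9.1 and assumed to apply in 9.6.2.
- The 20% prevalence is assumed to apply per participant to margins over 3 mm. Section 9.3 does not say so.
- All scans are readable, and true sensitivity is 91%.

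**Each look alone.** Expected positives are 0.20 × N. The rule trips when X/n < 0.85, with X ~ Binomial(n, 0.91).

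| Participants | Positives | Trips if detected ≤ | Probability |
|---|---|---|---|
| 50 | 10 | 8 | 22.5% |
| 150 | 30 | 25 | 12.8% |
| 300 | 60 | 50 | 4.1% |
| 500 | 100 | 84 | 1.7% |

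First row: 1 − 0.91¹⁰ − 10 × 0.91⁹ × 0.09 = 1 − 0.3894 − 0.3851 = 0.2254. Nine of ten (90%) passes and eight of ten (80%) trips, so two misses suffice. The 95% Wilson interval for 8/10 is 49% to 94%, which contains both 85% and 91%.

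**Cumulative probability of at least one trip at a true 91%.**

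| Basis | Four looks (50/150/300/500) | Three looks (150/300/500) |
|---|---|---|
| 20% prevalence, fixed positives (exact) | 22.5, 27.5, 28.3, 28.6% | 12.8, 14.0, 14.4% |
| 20% prevalence, random positives (1,000,000 runs) | 23, 28, 30, 30% | 13, 15, 16% |
| 10% prevalence, random positives, final value | 40% | 26 to 27% |

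With fixed positives and assumed prevalence from 5% to 30%, the four-look figure runs from 21% to 45%. It is not monotone, because small counts make the threshold jump.

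**Effect of indeterminate results.** Suppose 5% of results in positives are indeterminate (an assumption). Effective sensitivity is then 0.91 × 0.95 = 86.5%, and the four-look figure at 20% prevalence is 62% with fixed positives and 65% with random positives.

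**What an uncertainty-based trigger would do.** As an example, trip at 150/300/500 when the posterior probability (flat prior) that sensitivity is below 85% reaches 0.80.

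| | Raw rule, 20% prevalence | Posterior rule, 20% | Posterior rule, 10% |
|---|---|---|---|
| False trigger at true 91% | 16% | 4.5% | 10% |
| Detects true 80% by 500 | 94% | 81% | 72% |
| Detects true 80% at 150 | 74% | 52% | 46% |

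At a true 80% and 20% prevalence, the raw rule also gives about a 61 to 62% chance of a flag at the 50-participant look. The example rule has no action at that look.

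**The case against.** Four objections deserve weight.

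1. **In two of the three statements a trip is not a stop.** Where a missed margin is the main danger, a sensitive trigger for a review may be deliberate caution. This stands: under 3.3 and 9.1 the 16% to 30% is only the chance of an unneeded review.
2. **Section 9.6.2 has no number in the text at hand.** The blank may be lost text and is not an error in itself. A reader might infer that 9.6.2, as printed, ends an adequate trial on two missed margins. It does so only if 85% is meant.
3. **This is an estimation study.** "The sample size was calculated to estimate the sensitivity of the LaserSAFE technique with a 95% confidence interval"; no hypothesis test is stated. The form of the criterion and its operating characteristics are commonly left to an analysis plan, so their absence from the protocol is not a fault in itself. That also stands, but it does not remove a contradiction within the protocol.
4. **A different trigger costs detection.** The last table confirms this, so the posterior rule is an option and not a correction.

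Two other strong readings fail. One might attach the 30% to the look with about 10 positives; that look alone gives about 23%, and 30% is the total over four looks. One might also count section 9.2 as a further conflict, but its looks at 150, 300 and 500 belong to the cut-off rule for secondary resection.

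**Conclusion.** The contradiction is in the current text and must be resolved: the sections disagree on the number of looks and on the consequence, and 9.6.2's futility label does not fit the purpose given in 9.1.

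The numerical criticism is conditional. If 9.6.2 is meant as a mandatory stop at 85%, a test with the planned 91% sensitivity would be stopped with probability of about 23% at the first look, 30% over four looks and 16% over three. At 10% prevalence the cumulative figures are 40% and 26 to 27%. Counting indeterminate results as false negatives raises all of these. If the wording of 3.3 and 9.1 governs, the same numbers describe unneeded reviews, which is a much smaller cost.

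The figures count positive participants, as section 9.3 does. The Study Summary describes the primary analysis per side, and bilateral positives would change the counts.

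**What to change.** - Reconcile 3.3, 9.1 and 9.6.2 to one set of looks, one threshold and one consequence, and call it a safety rule.
- If a mandatory stop is kept, do not base it on the bare point estimate at the 50-participant look. Use a criterion that carries uncertainty, for example a one-sided bound or a posterior probability against 85%, counted in the unit of the primary analysis.
- If the raw 85% trigger is kept, let it lead to a review only.
- In either case state the false-trigger and detection probabilities at each look and over a range of prevalence.
- Fix the rule before the first interim look, rather than at any time before recruitment ends.

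The cost is protocol wording and a short simulation. An uncertainty-based trigger reacts more slowly to a real shortfall, as the working shows, and this should be stated openly. The choice of criterion, and whether the 50-participant look is descriptive only, is the sponsor's.
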